1 PROTOCOL SUMMARY

[figure not shown]
1.1 SYNOPSIS

Title:	Phase II Trial of Effect of Leptin Therapy in Severe Insulin Resistance
Study Description:	Patients with mutations of the insulin receptor have diabetes that is challenging to control with conventional therapies, leading to early morbidity and mortality. We hypothesize that recombinant leptin (metreleptin) in these patients will improve glycemia control.
Objectives:	Primary Objective : To determine if 1 year of metreleptin will improve glycemia control in patients with genetic defects of the insulin receptor. Secondary Objectives : To determine mechanisms by which metreleptin improves glycemia.
Endpoints:	Primary Endpoint : Hemoglobin A1c. Secondary Endpoints : fasting plasma glucose, fasting insulin/C-peptide, glucose/insulin/C-peptide area under the curve during oral glucose tolerance test.
Study Population:	20 male or female patients with mutations of the insulin receptor, age ≥ 5 years, at the NIH Clinical Center
Phase:	2
Description of Sites/Facilities	
Enrolling Participants:	NIH Clinical Center
Description of Study Intervention:	Open label study of metreleptin, 0.2 mg/kg/day (max dose 0.24 mg/kg/day).
Study Duration:	Indefinite as long as patients demonstrated benefit
Participant Duration:	12 months (may be extended if patient demonstrates benefit)

Abbreviated Title: Effects of leptin in insulin resistance

Version Date: AM N ver. (approved 10/21/20); rev for AM O (5/5/21)

1.2 SCHEMA

1.3 SCHEDULE OF ACTIVITIES (SOA)

Baseline Visit (3-4 days): Patients will be admitted to the research center.

They will have their history and physical examination completed on the day of admission. Following a 12 hour fast, the OGTT will be performed. In addition, patients' capillary blood glucose will be measured before each meal and at bedtime. 24-hour glucosuria (and other 24 hour urine studies) will also be determined. After baseline testing has completed, patients will be trained in the proper storage, preparation, and administration of metreleptin injection, and will begin metreleptin injections subcutaneously during the hospitalization. Therapy will begin at determined efficacious dose for this group of patients of (0.2 mg/kg/day for male and female patients). For patients who reside outside the US, sufficient drug supply will be sent home with the patient to last until the next scheduled visit. For patients who reside within the US, a 3 month supply of drug will either be sent home with the patient or shipped to the patient's home.

Months 6 and 12 and every 6 months thereafter (3-4 days): At the end of 6 months, patients will return to the Clinical Center for collection of the same data obtained at baseline. For patients for whom it is challenging to travel to the Clinical Center every 6 months (i.e. ex-US patients), visits may be conducted every 12 months after the first year per investigator discretion. In the event that circumstances beyond our control preclude the travel of one or more of the study participants to the NIH Clinical Center for a visit, or otherwise would put their health at greater risk (i.e. epidemic or pandemic), we will endeavor to establish capabilities for remote visits. Specifically, the study team will request local laboratory studies to be done, to include, at a minimum, basic chemistry panel, CBC with diff, hemoglobin A1c, and pregnancy testing in female subjects with reproductive capacity, and conduct a telehealth/telephone visit with the patient. Telehealth/telephone visits will adhere to HHS guidance (<https://www.hhs.gov/hipaa/for-professionals/special-topics/emergency-preparedness/notification-enforcement-discretion-telehealth/index.html>) and can use all telehealth modalities under the good faith provision during a pandemic/epidemic as allowed by HHS for care of study participants.

At each follow up visit, for patients who reside outside the US, sufficient drug supply will be sent home with the patient to last until the next scheduled visit. For patients who reside within the US, a 3 month supply of drug will either be sent home with the patient or shipped to the patient's home (US patients only).

Unscheduled visits, due to safety or clinical care, may also be conducted remotely through telehealth/telephone and may include offsite laboratory and radiologic studies and/or in conjunction with a local physician with the supervision of the study PI. Laboratory and imaging results will be sent to the study team for safety monitoring and clinical care. During a pandemic affecting patient travel, serial missed research collections will not be considered major study deviations and will be reported to the IRB at the time of continuing review. Laboratory and imaging results obtained outside of the NIH may be incorporated into the study data set for both safety and efficacy.

During this time, patients remain on the full predicted dose. At each of these subsequent visits, the patients will have their blood drawn collecting the same labs that were obtained at baseline, and including serial metabolic testing such as the OGTT.

Abbreviated Title: Effects of leptin in insulin resistance

Version Date: AM N ver. (approved 10/21/20); rev for AM O (5/5/21)

If after 12 months of treatment it is determined by the principal investigator that the patient has shown improvement metabolically (improved HgbA1c, FBS, fasting insulin level), we will continue to follow the patient indefinitely on leptin therapy until such time that the leptin is approved through the FDA and/or the patient does not wish to continue on the study.

The study will involve an initial week hospitalization for each recruited patient. Thereafter, the patients will return to the Clinical Center as in-patients for assessment and data collection in accordance with the program every 6-12 months. Pre-existing glucose lowering therapies will be adjusted as needed to prevent hypoglycemia per standard clinical practice by communication between qualified study staff and the patient (telephone, telehealth, etc.). Patients taking insulin are asked to check their blood sugars at least 2 times a day (before breakfast and before another meal or at bedtime). Patients not taking insulin are not asked to routinely monitor their glucose levels while at home.

Procedures	Baseline	6 months	1 year	Q6 months (after 1 st year)	Q12 months (after 1 st year)
Informed consent	x				
Demographics	x				
Diabetes antibodies	x				
Medical/interim history	x	x	x	x	x
Physical exam (including height and weight)	x	x	x	x	x
Vital signs	x	x	x	x	x
Height	x	x	x	x	x
Weight	x	x	x	x	x
Leptin level	x	x	x	x	x
Fasting labs (glucose, insulin, C-peptide, HbA1c, chemistry, CBC/diff, hormones, bone turnover markers, inflammatory markers)	x	x	x	x	x
Oral glucose tolerance test	x	x	x		x
Pelvic ultrasound	x	x	x		x
Thyroid ultrasound	x	x	x		x
24 hour urine studies	x	x	x	x	x

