3. Antibodies to recombinant human leptin: Development of anti-drug antibodies occurs in the majority of patients treated with metreleptin. In rare cases (<5%), antibodies with in vitro neutralizing activity to leptin may occur. Neutralizing antibodies could inhibit endogenous leptin action and/or result in loss of metreleptin efficacy.
4. Hypoglycemia: Metreleptin administration may increase the risk of hypoglycemia in patients treated with insulin or insulin secretagogues by improving insulin sensitivity. Patients will be cautioned about the possibility of hypoglycemia and all patients will receive education about signs and symptoms of hypoglycemia within the first week of the study

spent in the hospital. Diabetic patients will be measuring their glucose concentrations four times a day throughout the study and background therapy will be tailored to prevent hypoglycemia. Also we will explain this potential risk to the local physicians caring for the patients.

5. **T-cell lymphoma:** T-cell lymphoma has occurred in patients with acquired generalized lipodystrophy, both with and without metreleptin treatment. There is no data to support an increased risk of T-cell lymphoma (with or without metreleptin) in patients with mutations of the insulin receptor who may participate in this study.
6. **Autoimmunity:** Autoimmune disorder progression has been observed in patients with lipodystrophy treated with metreleptin, although a causal relationship with metreleptin has not been established. There is no data to support an increased risk of autoimmunity or autoimmune disease progression (with or without metreleptin) in patients with mutations of the insulin receptor who may participate in this study.

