5.3 INCLUSION OF VULNERABLE PARTICIPANTS

Children: Patients with mutations of the insulin receptor, particularly those with biallelic mutations causing Rabson Mendenhall Syndrome, typically develop diabetes in childhood, with death often occurring in the second or third decade of life. Because this is a pediatric condition, most patients enrolled in this study will be <18 years of age. Children <5 years of age may not enroll. In our experience with the younger children, we find that their participation in serial blood tests improves greatly when they are at least 5 years of age. Also, in our experience with the patients with mutations of the insulin receptor, their initial insulin resistance is manifested as

Abbreviated Title: Effects of leptin in insulin resistance

Version Date: AM N ver. (approved 10/21/20); rev for AM O (5/5/21)

extreme hyperinsulinemia and hypoglycemia (rather than hyperglycemia) in the younger patients. We would not want to treat a young child experiencing chronic hypoglycemia.

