6.1.2.3 Dose Modifications

Patients will monitor body weight at home weekly for the first 3 months of treatment. In addition, weight is monitored at each follow up visit. Doses of metreleptin will be adjusted based on body weight to maintain a consistent dose of metreleptin within the range of 0.18-0.24 mg/kg/day. If body weight decreases by more than 15%, then a dose reduction (by 0.02 mg/kg/day) will be made. If a dose change is made, patients will monitor body weight at home monthly for the next 3 months and additional dose adjustments will be made as needed.

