6.5 CONCOMITANT THERAPY

If patients are on glucose lowering therapy at the beginning of the study, metreleptin will be added to the existing therapy. Patients' previous therapy will be tapered to prevent hypoglycemia if necessary but doses of glucose lowering medications will not be increased during the first year of the study (at the time the primary outcome is assessed.) Glucose lowering therapies may be adjusted as clinically indicated after the first year of treatment. Patients will be standard clinical instruction about signs and symptoms of and instructions to relieve hypoglycemia.

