7.2 PARTICIPANT DISCONTINUATION/WITHDRAWAL FROM THE STUDY

Participants are free to withdraw from participation in the study at any time upon request.

An investigator may discontinue or withdraw a participant from the study for the following reasons:

- Adverse events that are not readily explained by other causes unrelated to current protocol. Examples include:
 - Systemic life-threatening allergic reaction to metreleptin
 - Other significant medical issues that will, in the judgment of the investigators, preclude safe completion of the study.
- Noncompliance with self-monitoring requirements and Clinical Center visits
- Development of any medical problem listed in the exclusion criteria
- Significant medical issues that will in the judgment of the investigators preclude safe completion of the study. If an investigator feels it is in the subject's best interest to terminate participation, the detailed reasoning behind this decision will be documented. Examples include change in benefit-risk ratio of metreleptin treatment for an individual patient, such as:
 - Loss of efficacy of metreleptin (e.g. due to development of neutralizing antibodies)
 - Development of a medical condition that might increase risks associated with metreleptin (e.g. T-cell lymphoma, high risk thyroid cancer) in a patient not receiving dramatic clinical benefit
 - More than 8% drop in hematocrit and discontinuation recommended by Hematology Service
 - WBC count < 2500 or absolute neutrophil count < 1000 and discontinuation recommended by Hematology Service
- Death

The reason for participant discontinuation or withdrawal from the study will be recorded in the medical record.

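### Sections 2.3.1 and 1.3 give incompatible home glucose rules for diabetic patients not on insulin, and 1.3 leaves out insulin secretagogue users

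*Combined protocol and SAP*

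**What the plan says.** Two sections of the combined protocol and SAP set a home glucose rule.

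- **Section 2.3.1, item 4 (Hypoglycemia).** It names who is at risk: "Metreleptin administration may increase the risk of hypoglycemia in patients treated with insulin or insulin secretagogues by improving insulin sensitivity". It then gives the mitigation: "Diabetic patients will be measuring their glucose concentrations four times a day throughout the study and background therapy will be tailored to prevent hypoglycemia".
- **Section 1.3 (Schedule of activities).** "Patients taking insulin are asked to check their blood sugars at least 2 times a day", with one check before breakfast and the other before a later meal or at bedtime. The next sentence reads: "Patients not taking insulin are not asked to routinely monitor their glucose levels while at home".

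Three other sections bear on the point. Under 6.5, metreleptin is added to whatever glucose-lowering therapy the patient already takes, and "previous therapy will be tapered to prevent hypoglycemia if necessary but doses of glucose lowering medications will not be increased during the first year". The exclusion list in 5.2 does not mention secretagogues. Section 7.2 lists "Noncompliance with self-monitoring requirements and Clinical Center visits" among the reasons for which an investigator may withdraw a participant, without saying which requirements are meant.

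**The concern.** The risk section and the schedule describe different safeguards against the same drug risk. The risk section ties monitoring to having diabetes; the schedule ties it to taking insulin. A diabetic patient who is not on insulin falls on opposite sides of the two rules.

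The schedule's dividing line also does not match the risk statement. Section 2.3.1 names two drug classes that raise the risk on metreleptin, and 1.3 asks for checks in only one of them.

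What is at stake is safety and conduct. The risk section, on which an ethics board would rely, promises more than the schedule asks for. Staff also have two texts from which to teach patients and judge compliance.

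**Working it through.** There is no planned figure to reproduce, and no statistical calculation applies. The check sets the two rules side by side for each kind of patient the protocol can enroll.

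| Patient | 2.3.1, item 4 | 1.3 | Can both be met? |
|---|---|---|---|
| Diabetic, on insulin | 4 a day | at least 2 a day | Yes, by checking 4 times |
| Diabetic, on a secretagogue but not insulin | 4 a day | no routine home checks | No |
| Diabetic, on neither | 4 a day | no routine home checks | No |
| Not diabetic, not on insulin | no rule stated | no routine home checks | No conflict |

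1. **Could the four checks refer to inpatient stays only?** Section 1.3 does have capillary glucose measured before meals and at bedtime during the baseline admission. But 2.3.1 applies its rule for the whole study, and patients are at home between visits that are 6 to 12 months apart. The inpatient reading does not fit.
2. **Does any section say which rule prevails?** None was found in the available text.
3. **Can the affected patients enroll?** Yes. Inclusion criterion 4 does not require insulin use, and 1.3 itself provides for patients not taking insulin. Sections 5.2 and 6.5 leave secretagogue users eligible and on their existing drug.
4. **How many are affected?** The documents do not say. With an accrual ceiling of 20, the number of secretagogue users not on insulin could be anything from 0 to 20. The number of diabetic patients off insulin is not given either.

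**The case against.** The strongest reply is that this is a wording mismatch, with the schedule as the working instruction and 2.3.1 as background narrative. Several parts of that reply stand.

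- For insulin users there is no contradiction. At least 2 is a floor, and four checks meet it.
- Section 1.3 rules out only routine checks. It does not bar checks prompted by symptoms or a change in therapy, and it has background therapy adjusted through contact between staff and patient under usual clinical practice.
- Nothing shows that any participant takes a secretagogue without insulin. The risk statement belongs to a list drawn from other metreleptin populations.
- Other safeguards apply to everyone or to the drug generally: hypoglycemia education, notice to local physicians, unscheduled remote visits and withdrawal for safety.

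The reply does not remove the conflict for diabetic patients off insulin. The schedule is the more specific text, but the protocol never says that it overrides the risk section, and the sentence in 2.3.1 states what patients will do. The other safeguards do not settle which home rule holds.

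A reader might infer three stronger points, which the documents do not support.

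- *That tapering will be done blind and cannot be reversed before the 12-month HbA1c.* Section 6.5 bars dose increases in year 1, but it does not say whether restoring a tapered dose counts as one. Nor does the protocol prescribe tapering without readings.
- *That a patient who follows the schedule would be withdrawn under 7.2.* That provision is discretionary, and its term is undefined. It might equally mean the home weights in 6.1.2.3 ("Patients will monitor body weight at home weekly for the first 3 months of treatment").
- *That non-diabetic children are left unprotected.* The remark in 5.3, "We would not want to treat a young child experiencing chronic hypoglycemia", helps explain the minimum age of 5 years. It does not show that an enrolled non-diabetic child is hypoglycemic or put at risk by the drug.

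**Conclusion.** The point holds as an internal inconsistency in the safety text. For diabetic patients not on insulin the two rules are incompatible: four checks a day against no routine checks. For insulin users the gap is only in the stated minimum. The schedule also omits secretagogue users not on insulin, who belong to a group that the protocol itself names as at raised risk.

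This rests on reading the unqualified reference to diabetic patients in 2.3.1 as covering those off insulin, and on no other text settling the matter. The number of patients affected is unknown, and for secretagogue users not on insulin it may be zero. Multiplying checks by days would measure the difference in wording, not any harm, so no such count is offered. Neither the HbA1c analysis nor the sample size in 9.2 is touched. The text should be corrected, but the primary result is not in doubt.

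**What to change.** Write one rule and use it in all three places.

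- **Section 1.3:** ask patients taking insulin or an insulin secretagogue to check at least 2 times a day, with the existing timing. Limit the sentence that asks for no routine monitoring to patients taking neither insulin nor an insulin secretagogue.
- **Section 2.3.1, item 4:** replace the whole monitoring sentence with the same rule. Changing only the number would leave diabetic patients as its subject, and so leave a conflict with 1.3.
- **Section 7.2:** have the self-monitoring ground refer to this rule, without displacing the home weights in 6.1.2.3.

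The cost is a short amendment, plus a meter, strips and two finger sticks a day for any secretagogue user not on insulin. No visit, laboratory test or exclusion is added.

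The amendment should tell the IRB plainly that the safeguard now stated in 2.3.1 falls from 4 to at least 2 checks a day for insulin or secretagogue users, and from 4 to none for diabetic patients on neither. If the team prefers four, it should appear in both sections; under this rule the drop to none for diabetic patients on neither class would remain and would still need disclosure.

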2 INTRODUCTION

2.1 STUDY RATIONALE

Patients with extreme insulin resistance caused by biallelic pathogenic variants of the insulin receptor (Rabson Mendenhall syndrome) develop diabetes in childhood that is difficult to control with FDA-approved therapies, including insulin doses 50-fold higher than those typically used to treat diabetes. Thus, novel therapies that lower blood glucose independent of insulin-receptor signaling are needed. Recombinant human leptin (metreleptin) lowers blood glucose in patients with lipodystrophy and low leptin levels. Patients with Rabson Mendenhall syndrome also have low leptin as a result of low body fat (because insulin signaling is critical for adipogenesis), and thus are candidates for metreleptin therapy. In addition, the intracellular signaling cascades of leptin and insulin receptors overlap at PI3 kinase, suggesting that pharmacologic overstimulation of the leptin receptor might trigger intracellular insulin signal transduction. We therefore plan to test the safety and efficacy of metreleptin in patients with Rabson Mendenhall syndrome/

2.2 BACKGROUND

Type 2 diabetes is the most common form of diabetes, characterized by insulin resistance with inadequate compensatory insulin secretion, resulting in hyperglycemia. While type 2 diabetes is polygenic, there exist rare, monogenic conditions that cause severe forms of insulin resistance and diabetes. We have studied the more unusual syndromes of diabetes that are characterized by extreme forms of insulin resistance. All of these patients manifest severe hyperinsulinemia or have requirements for very large doses of insulin. The syndromes have been categorized under a variety of names. These include the following: type A insulin resistance and type B insulin resistance, which were first described in the NIDDK, and are characterized by abnormalities in the insulin receptor^{i,ii}. Other syndromes of a similar nature include the Rabson-Mendenhall syndrome and the various syndromes of lipodystrophy.

Therapy for all of these syndromes has been inadequate and the prognosis and mortality rate for all of these syndromes has been extremely high. We have been following a group of patients with severe insulin resistance due to mutations on their insulin receptor gene. A fraction of these patients are compound heterozygotes or homozygotes for a mutation in the insulin receptor gene. In addition to having diabetes that is very difficult to control starting at young ages, these patients also have a paucity of fat. Low leptin levels (leptin levels <3.0 ng/mL) is an observed metabolic abnormality in this group of patients among other findings (unpublished observations). These most severe patients have very limited longevity (some die before age 10 years and others die before age 30 from multiple etiologies starting from severe diabetic complications to pulmonary hypertension and heart failure).

In a pilot study of two patients with the Rabson-Mendenhall syndromes (caused by biallelic mutations of the insulin receptor), 02-DK-0060, “Efficacy of leptin therapy in severe insulin resistance: a pilot study,” we followed two children with Rabson-Mendenhall on 10 months of recombinant leptin therapy. During the 10 months of leptin therapy, the patients had dramatic improvements (40%) in their fasting hyperinsulinemia and (50%) hyperglycemia, and overall improvements in their %HgbA1c and glucose and insulin tolerance. Three months after the medication was withdrawn, the improvements observed had deteriorated to their pre-trial baseline [1]. A follow up report published in 2013 in 5 patients who participated in the current study demonstrated that A1c decreased from $11.4 \pm 1.1\%$ at baseline to $9.3 \pm 1.9\%$ after 6 months and

9.7±1.6% after 12 months of metreleptin (P=0.007) [2]. In patients treated for 10 years, A1c declined with each cycle of metreleptin and rose with each withdrawal.

